This study consists of a Phase 1 Dose Escalation Phase (DEP) and a Phase 2a Dose Expansion Phase (EXP). The DEP is a “3+3” dose escalation design to establish the MTD or the OBD of ALRN-6924. The EXP will enroll up to 5 distinct groups of patients with specific solid tumors and/or lymphomas to further investigate the clinical safety profile and potential efficacy of ALRN-6924 at the MTD, OBD, or in alternate dosing regimens.

In the Phase 2a EXP, peripheral T-cell lymphoma (PTCL) has been selected as one of the diseases to be further studied in up to 3 cohorts to identify the optimal dosing regimen.

Another Phase 2a EXP group will include patients with MDM2 amplified or MDM2/CDK4 co-amplified solid tumors who will receive ALRN-6924 in combination with palbociclib. As these agents have not previously been co-administered, a safety run-in of 6-8 patients will first be enrolled and evaluated by the sponsor and the primary investigators before further patients are permitted to enroll. Patients will receive ALRN-6924 at the previously determined recommended Phase 2 dose for the once-weekly administration schedule (3.1 mg/kg on Days 1, 8, and 15) and palbociclib at an oral dose of 100 mg daily for 21 days (one dose level below the approved oral dose of 125 mg) in a 28-day cycle. Doses of ALRN-6924 and palbociclib may be adjusted for safety or tolerability prior to enrolment of additional patients into this EXP group.

Treatment of patients in the dose escalation and the dose expansion phases of the study will continue until

unacceptable toxicity, patient or physician decision to discontinue therapy or disease progression that is either symptomatic, rapidly progressive, requires urgent intervention, or is associated with a decline in performance status.

TP53 Status Determination and Tumor Sampling Requirements

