- If a DLT is observed in 1 of 3 patients in a cohort at any dose level, then up to 6 patients total will be enrolled in the same DR at that dose level. If a DLT is observed in 2 or more patients in the expanded cohort, then no further dose escalation will occur, and the current dose will be defined as the MAD, unless the SRC decides that there is sufficient clinical uncertainty about the DLTs that warrants the enrollment of up to 6 additional patients. In the event of additionally enrolled patients, if a DLT is observed in 33% or more DLT-evaluable patients in the entire cohort, then no further dose escalation will occur, and the current dose will be defined as the MAD for the dosing regimen under consideration.
- After the MAD is defined, either the previously administered lower dose will be expanded to a total of 6 patients, or an intermediate dose (between the MAD and the previous dose level) will be investigated in a total of 6 patients. The highest dose tolerated in at least 5 of 6 patients (i.e. $<33\%$ of DLT-evaluable patients experiencing a DLT) will be defined as the MTD or OBD. Additional patients may be added to further explore the MTD or OBD prior to expansion.

The SRC may hold the dose (e.g., stop dose escalation) at their discretion and enroll additional patients until sufficient safety data are obtained to determine escalation of the current dose level or to confirm a certain dose level as an MTD or OBD.

Dose Level and Dose Regimen – Phase 2a dose expansions

Based on the safety, efficacy and PK/PD profile of ALRN-6924 from the dose escalation portion of the study as well as data from other clinical trials and preclinical data, three dosing regimens of ALRN-6924 administered as single agent therapy (DR-A, DR-B, DR-C) will be tested in Phase 2a EXP in PTCL to determine the optimal dosing regimen.

For patients with MDM2 amplified or MDM2/CDK4 co-amplified solid tumors, patients will receive ALRN-6924 in combination with palbociclib. Palbociclib will be administered at an oral dose of 100 mg daily (Days 1-21) in combination with ALRN-6924, which will be administered at 3.1 mg/kg on Days 1, 8, and 15 of a 28-day cycle (or as otherwise determined during the safety run-in period for this cohort).

The decision to begin palbociclib below the approved dose level of 125 mg is based on the frequency of required

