dose reductions, often due to neutropenia. The SRC may consider escalating to the approved palbociclib dose, if palbociclib-related toxicities are not prohibitive and patient benefit is expected to outweigh risk.

Dose Level and Dose Regimen – Phase 2a dose expansions:

Treatment Regimen	Drug and Dose Level	Infusion Days	Infusion Time	Additional notes
DR-A	ALRN-6924 3.1 mg/kg	1, 8, 15 of a 28-day cycle	1 hour (± 15 min)	At the end of the infusion, IV fluids (saline) or oral fluids (500 mL – 1000 mL) should be administered, unless clinically contraindicated.
DR-B	ALRN-6924 2.7 mg/kg	1, 4, 8, 11 of a 21-day cycle	1 hour (± 15 min)	At the end of the infusion, IV fluids (saline) or oral fluids (500 mL – 1000 mL) should be administered, unless clinically contraindicated.
DR-C	ALRN-6924 3.1 mg/kg [If 3.1 mg/kg is not well tolerated, lower doses may be tested starting at dose levels of -25%]	1, 3, 5 of a 21-day cycle	1 hour (± 15 min)	At the end of the infusion, IV fluids (saline) or oral fluids (500 mL – 1000 mL) should be administered, unless clinically contraindicated.
Combination with palbociclib	ALRN-6924 3.1 mg/kg [If 3.1 mg/kg is not well tolerated, up to two dose reductions of 25% may be tested]	1, 8, 15 of a 28-day cycle	1 hour (± 15 min)	At the end of the infusion, IV fluids (saline) or oral fluids (500 mL – 1000 mL) should be administered, unless clinically contraindicated.
	Palbociclib 100 mg [If 100 mg is not well tolerated, a reduced dose of 75 mg may be tested.]	1-21 of a 28-day cycle	Oral	Palbociclib should be administered with food. On days when both drugs are administered (Days 1, 8, and 15 of each cycle), palbociclib should be administered at least 6 hours after the infusion of ALRN-6924.

Intra-patient Dose Escalation – Phase 1 Dose Escalation

A patient's dose may be increased to that of a cohort that completed the first cycle without dose-limiting toxicity in $\geq 33\%$ of DLT-evaluable patients and that has not exceeded the MTD. Intra-patient dose escalations will be allowed provided that the patient completed at least two treatment cycles and did not experience study medication-related toxicity greater than Grade 2 (except for alopecia, electrolyte disturbances responsive to correction within 24 hours,

diarrhea, nausea, fatigue and vomiting that responds to standard medical care). Approval for intra-patient dose escalation must be obtained from the Medical Monitor.

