3.2 Study Overview

This is a Phase 1/2a open-label, multi-center, dose-escalation and dose expansion study designed to evaluate the safety, tolerability, PK, PD, and anti-tumor effects of ALRN-6924 administered by IV infusion once weekly for 3 consecutive weeks on Days 1, 8, and 15 of a 28-day cycle (Dose Regimen A or DR-A and DR-A-2), twice weekly for 2 consecutive weeks on Days 1, 4, 8, and 11 of a 21-day cycle (Dose Regimen B or DR-B), or three times weekly for one week on Days 1, 3, and 5 of a 21-day cycle (Dose Regimen C or DR-C) in patients with advanced solid tumors or lymphomas that are anticipated to express WT TP53.

This study consists of a Phase 1 Dose Escalation Phase (DEP) and a Phase 2a Dose Expansion Phase (EXP). The DEP is a “3+3” dose escalation design to establish the MTD or the OBD of ALRN-6924. The EXP will enroll up to 5 distinct groups of patients with specific solid tumors and/or lymphomas to further investigate the clinical safety profile and potential efficacy of ALRN-6924 at the MTD, OBD, or an alternative dosing regimen.

Peripheral T-cell lymphoma (PTCL) has been selected as one of the Phase 2a EXP groups to be further studied; up to 3 cohorts in PTCL may be studied in order to determine the optimal dosing regimen.

Another Phase 2a EXP group will include patients with MDM2 amplified or MDM2/CDK4 co-amplified solid tumors who will receive ALRN-6924 in combination with palbociclib. As these agents have not previously been co-administered, a safety run-in of 6-8 safety evaluable patients will first be enrolled to determine the optimal dosing regimen for the combination.

Treatment of patients in the dose escalation and the dose expansion phases of the study will continue until unacceptable toxicity, patient or physician decision to discontinue therapy, or disease progression that is either symptomatic, rapidly progressive, requires urgent intervention, or is associated with a decline in performance status. Patients receiving clinical benefit may continue on study after a discussion between the Principle Investigator and Medical Monitor.

Starting at Dose Level 4 (DEP), patients with a Human Papilloma Virus (HPV)-positive malignancy will be excluded from enrollment. This is owing to the fact that HPV-infected tumor cells continue to express the viral E6 protein, which is known to cause degradation of p53, hence rendering the expected ALRN-6924-mediated dual inhibition of MDM2/MDMX very unlikely to restore p53 function.

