Phase 2a – Dose Expansion in MDM2 Amplified or MDM2/CDK4 Co-amplified Solid Tumors (ALRN-6924 plus palbociclib)

Patients enrolled in this cohort must have MDM2 amplified or MDM2/CDK4 co-amplified solid tumors, as determined by local, commercial or central assays such as NGS, fluorescent in situ hybridization (FISH) or comparative genomic hybridization (CGH). However, all patients must have fresh or archival tissue submitted to the central laboratory for NGS testing. The central laboratory's results will determine the patient's official classification as MDM2 amplified, MDM2/CDK4 co-amplified, or neither MDM2 amplified nor MDM2/CDK4 co-amplified.

Mutational analysis of TP53 is not required for this cohort, as TP53 mutations are extremely rare among patients with MDM2 amplifications. However, patients with known mutations or deletions of TP53 will be excluded from study participation. Likewise, patients with known Rb mutations will be excluded, as the cell cycle arrest and senescence response by palbociclib's CDK4/6 inhibition is mediated by Rb, and loss or functional mutation of Rb is specifically associated with resistance to palbociclib.³⁰

Enrollment of the first 3 patients in this cohort will be separated in time by at least one week each, to assess for unexpected acute toxicities related to administration of the treatment regimen. ALRN-6924 will be administered by IV infusion over 1 hour (\pm 15 min) on Days 1, 8, and 15 of a 28-day cycle. Palbociclib

will be administered at an oral dose of 100 mg daily for 21 days (one dose level below the approved oral dose of 125 mg) in the same 28-day cycle. A safety run-in group of 6-8 patients will first be enrolled and evaluated before further patients are permitted to enroll. In the event that this regimen is not determined to be safe or tolerable at these dose levels, the dose of ALRN-6924 will be decreased by 25% and/or the dose of palbociclib will be decreased by one dose level (to 75 mg/day), as needed based on the pattern of toxicities encountered. An additional 6-8 patients will be assessed in a safety run-in using the reduced dose level before further enrollment is permitted. One subsequent reduction of the ALRN-6924 dose by 25% may be implemented, if safety and tolerability are still not acceptable. Once the safety run-in is complete, all subsequent patients will be enrolled at the recommended dose level.

Phase 1 and Phase 2a

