ALRN-6924 and palbociclib have not previously been co-administered in humans. Therefore, for the Phase 2a cohort of patients with MDM2 amplified or MDM2/CDK4 co-amplified solid tumors, a safety run-in group of 6-8 patients will first be enrolled and evaluated by the sponsor and the primary investigators before further patients are permitted to enroll. The SRC will use the DLTs defined in Phase 1 and the toxicity profile of palbociclib (in accordance with the package insert) as a guide for assessing safety.

Enrollment of the first 3 patients in this cohort will be separated in time by at least one week each, to assess for unexpected acute toxicities related to administration of the treatment regimen. Patients will receive ALRN-6924 at the previously determined recommended Phase 2 dose for the once-weekly administration schedule (3.1 mg/kg on Days 1, 8, and 15) and palbociclib at an oral dose of 100 mg daily for 21 days (one dose level below the approved oral dose of 125 mg) in a 28-day cycle. In the event that this regimen is not determined to be safe or tolerable at these dose levels, the dose of ALRN-6924 will be decreased by 25% and/or the dose of palbociclib will be decreased by one dose level (to 75 mg/day), as needed based on the pattern of toxicities encountered, and an additional 6-8 patients will be assessed in a safety run-in using the reduced dose level, before further enrollment is permitted. Subsequent reductions of the ALRN-6924 dose by 25% may be implemented if safety and tolerability are still not acceptable. The decision to begin palbociclib below the approved dose level is based on the frequency of required dose reductions, often due to neutropenia. The SRC may consider adjusting to the approved palbociclib dose, if palbociclib-related toxicities are not prohibitive and patient benefit is expected to outweigh risk. Once the safety run-in is complete, all subsequent patients will be enrolled at the recommended dose level.

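### Palbociclib may be raised from 100 to 125 mg in the ALRN-6924 combination with no required run-in, patient number or enrolment hold at 125 mg, although the starting level and first reduced level each require 6-8 patients with enrolment held

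*Protocol*

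**What the plan says.** **Starting level.** The combination starts at ALRN-6924 3.1 mg/kg on Days 1, 8 and 15 with palbociclib 100 mg on Days 1-21 of a 28-day cycle. Protocol 3.2 and 5.7.2 call for 6-8 patients to be evaluated before anyone else enrols, with the first three separated by at least a week. Section 5.7.2 gives the reason: the two drugs have not been given together in humans.

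**Stepping down.** If the starting level is not tolerable, ALRN-6924 falls by 25%, palbociclib falls to 75 mg, or both. Section 3.2 then says: "An additional 6-8 patients will be assessed in a safety run-in using the reduced dose level before further enrollment is permitted". Section 5.7.2 matches it: "an additional 6-8 patients will be assessed in a safety run-in using the reduced dose level, before further enrollment is permitted". For later steps 5.7.2 says only "Subsequent reductions of the ALRN-6924 dose by 25% may be implemented if safety and tolerability are still not acceptable" and does not restate the run-in.

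**Stepping up.** Section 5.7.2 says: "The SRC may consider adjusting to the approved palbociclib dose, if palbociclib-related toxicities are not prohibitive and patient benefit is expected to outweigh risk". The synopsis uses a more direct verb: "The SRC may consider escalating to the approved palbociclib dose", under the same condition. The next sentence of 5.7.2 says that, after the run-in is complete, everyone enrolled later receives the recommended dose.

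**General wording.** The synopsis says doses "may be adjusted for safety or tolerability prior to enrolment of additional patients into this EXP group", and gives the regimen as the stated doses "or as otherwise determined during the safety run-in period for this cohort". Section 3.2 says the run-in patients "will first be enrolled to determine the optimal dosing regimen for the combination".

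**The concern.** The checkpoint is explicit for the first move to lower exposure and absent for the only move to higher exposure. The reason given for the 100 mg run-in, no prior co-administration, applies equally to 125 mg. The condition attached to the increase is a judgement about toxicity and expected benefit. It can be met on 100 mg data alone.

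A site or SRC following the text could therefore complete 6-8 patients at 100 mg, name 125 mg as the recommended dose, and enrol the rest of the cohort there. The protocol would not require any group to be assessed through a cycle at 125 mg first. The approval of 125 mg does not answer this: Protocol 1.6 describes it in breast cancer with an aromatase inhibitor or fulvestrant. This cohort takes mixed solid tumors from age 12 (Protocol 4.5) and adds an investigational drug.

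**Working it through.** The documents give no operating characteristic for the run-in, so there is no plan figure to reproduce. The check compares the rules by level and then counts patients.

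**1. Rules by combination level**

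| Level | Run-in size stated | Enrolment hold stated | Where |
|---|---|---|---|
| 3.1 mg/kg + 100 mg (start) | 6-8 | Yes | Protocol 3.2, 5.7.2, 8.10.1, synopsis |
| First reduced level | further 6-8 | Yes | Protocol 3.2, 5.7.2 |
| Later ALRN-6924 reductions | not restated | not restated | Protocol 3.2, 5.7.2 |
| Palbociclib 125 mg | none | none | Protocol 5.7.2, synopsis |

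**2. Does another section fill the gap?**

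- 5.6 governs single-agent dose escalation. Its Cycle 1 condition names DR-A, DR-A-2 and DR-B only.
- 5.7.3 covers intra-patient escalation in Phase 1 only.
- 8.6 triggers expansion-phase run-in reviews by accrual to a target number. It sets no target for 125 mg, so it acts there only if a run-in exists.
- 8.10.1 lists escalation conditions for the three single-agent regimens. Its combination paragraph repeats the initial 6-8 patient run-in.
- The dosing tables in 5.3 and the synopsis list palbociclib 100 mg and 75 mg, not 125 mg. Section 3.2 does not mention the increase.

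None of these sets a run-in or hold at 125 mg.

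**3. Size of the dose step**

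125/100 - 1 = +25%. Per 21-day course: 21 x 100 = 2100 mg; 21 x 125 = 2625 mg.

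**4. Patients who could enrol at 125 mg without a required hold**

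Inputs: cohort size N of about 15-25 (Protocol 3.3); first run-in of 6-8. Assumptions: the SRC raises the dose right after the first run-in, and every remaining patient starts at 125 mg.

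If run-in patients count toward N, the number is N minus 8 to N minus 6:

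- N = 15: 15 - 8 = 7 to 15 - 6 = 9
- N = 20: 20 - 8 = 12 to 20 - 6 = 14
- N = 25: 25 - 8 = 17 to 25 - 6 = 19

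Overall 7-19. If run-in patients are additional to N, the range is 15-25. If 125 mg is tested in the run-in, or never used, it is 0.

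**5. Patients left to enrol after a 125 mg run-in of 6-8**

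If both run-ins count toward N, the number is N - 16 to N - 12, floored at 0:

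- N = 15: 0-3
- N = 20: 4-8
- N = 25: 9-13

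If the 100 mg run-in is additional: 15 - 8 = 7 to 25 - 6 = 19.

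**6. What 6-8 patients can show (illustration only)**

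The documents give no dose-limiting toxicity (DLT) rate at 125 mg, so the rate p is assumed across a range. P(at least 2 DLTs) = 1 - (1-p)^n - n p (1-p)^(n-1).

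| Assumed p | n = 6 | n = 8 |
|---|---|---|
| 20% | 0.345 | 0.497 |
| 33% | 0.642 | 0.799 |
| 40% | 0.767 | 0.894 |
| 50% | 0.891 | 0.965 |

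A run-in of the protocol's own size would often reveal a high rate, but not reliably a moderate one.

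**The case against.** The best defence is that 125 mg belongs to the run-in. The permission in 5.7.2 stands between the run-in dose reductions and the sentence that closes the run-in, and the run-in's stated purpose is to settle the combination regimen. On that reading, any move to 125 mg is tested before the dose is fixed. This is possible, but no sentence requires it. The same placement also supports running 6-8 patients at 100 mg and then recommending 125 mg. The synopsis sentence on adjusting doses before more patients enrol sets an order, adjust and then enrol, and asks for no evaluation at the adjusted dose.

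The second defence is ongoing oversight. Section 8.10.1 has investigators and the Medical Monitor review toxicities in all patients by regular teleconference, and says escalations rest on observed toxicity. Section 8.10.2 has the Medical Monitor review safety data as they arrive. The SRC has the Phase 1 DLTs and the palbociclib label as its guide. This stands. A reader might infer that 7-19 patients would be treated with nobody looking at 125 mg data as a group; the documents do not support that. What is missing is a required evaluation and an enrolment hold.

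A reader might also infer that 125 mg is likely to be unsafe with ALRN-6924. That is not shown. Marrow overlap is plausible: palbociclib starts low because dose reductions are often for neutropenia, and ALRN-6924 gave anemia and neutropenia DLTs at 4.4 mg/kg over 2 hours (5.7.1). With the 1-hour infusion used here, however, the DLTs were hypotension and hepatobiliary laboratory abnormalities at dose level 7, and fatigue in 1 of 6 patients at 3.1 mg/kg (5.7.2). Section 1.4.4.2 expects no pharmacokinetic interaction.

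**Conclusion.** The gap is real and worth closing. The protocol permits a 25% palbociclib increase in a new combination on a qualitative condition, with no run-in, number or hold at the higher level, while requiring all three at the starting level and first reduced level.

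Up to 7-19 patients (15-25 if run-in patients are additional) could enrol at 125 mg without a required hold. This upper limit assumes an immediate increase after the first run-in and all remaining patients starting at 125 mg. It concerns newly enrolled patients only; the protocol does not say whether patients already on treatment could also be raised. The number is 0 if the SRC tests 125 mg within the run-in or never uses it. It is not an estimate of toxicity, nor of patients treated without any safety review. The contrast with dose reduction also applies only to the first reduced level, since later ALRN-6924 reductions carry no restated run-in either.

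**What to change.** In Protocol 5.7.2 and the synopsis, add a sentence such as: *If the SRC increases palbociclib to 125 mg, 6-8 patients will be assessed in a safety run-in at that level, and the SRC will review them through Cycle 1 using the same DLT guide, before any further patient enrols.* For consistency, carry it into 3.2 and add 125 mg to the dosing tables in 5.3 and the synopsis. The size is the protocol's own, the Cycle 1 review mirrors the DR-C run-in, and the decision to raise the dose stays with the SRC.

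The cost is amendment wording, and nothing more if the dose is never raised. If it is raised, the study accrues a 6-8 patient run-in and holds enrolment for about one 28-day cycle. In a 15-patient cohort where run-in patients count toward the total, only 0-3 patients would remain after the two run-ins, so the sponsor should settle whether run-in patients count.

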5.7.3 Intra-Patient Dose Escalation- Phase 1 Dose Escalation

A patient's dose may be increased to that of a cohort that completed the first cycle without dose-limiting toxicity in $\geq 33\%$ of DLT-evaluable patients and that has not exceeded the MTD. Intra-patient dose escalations will be allowed provided that the patient completed at least two treatment cycles and did not experience study medication-related toxicity greater than Grade 2 (except for alopecia, electrolyte disturbances responsive to correction within 24 hours, diarrhea, nausea, fatigue and vomiting that responds to standard medical care). Approval for intra-patient dose escalation must be obtained from the Medical Monitor.

5.8 Dose and Schedule Adjustments for Toxicity

5.8.1 Dose Modifications – Phase 1 dose escalation (ALRN-6924 administered as single agent therapy)

In the event a Grade 4 AE considered related to ALRN-6924 is observed, the patient must be discontinued from study treatment. Exceptions include Grade 4 neutropenia lasting <3 days, and emesis, diarrhea or electrolyte abnormalities that resolve within 2 days on optimum treatment. For these exceptions, treatment may be delayed for up to 2 weeks to allow resolution of the toxicity (i.e., return to Grade ≤ 1 or baseline), followed by re-treatment at a reduced dose. Two dose reductions are permitted; a third dose reduction will require evidence of clinical benefit and approval by the Medical Monitor. Relevant labs should be repeated as medically indicated.

In the event a Grade 3 AE considered related to ALRN-6924 is observed (exceptions are Grade 3 fatigue, nausea, emesis, diarrhea or clinically insignificant electrolyte abnormalities that resolve within 2 days on optimum treatment), treatment may be delayed for up to 2 weeks to allow resolution of the toxicity, followed by re-treatment at a reduced dose. Two dose reductions are permitted, a third dose reduction will require evidence of clinical benefit and approval by the Medical Monitor. Relevant labs should be repeated as medically indicated.

Dose modifications for re-treatment following related Grade 3 and Grade 4 AEs (as permitted): patients will be re-treated at the preceding dose level (per Figure 9).

For other clinically significant AEs, treatment may be delayed by up to 2 weeks to allow for the resolution of AEs to an acceptable level, and may continue treatment at a reduced dose level as described above at the discretion of the Investigator in consultation with Sponsor's Medical Monitor. If a patient experiences multiple AEs, decisions on dosing delay or dose reduction will be based on the most severe AE. Any patient who experiences recurrent, clinically significant AE after one dose reduction may undergo one additional dose reduction. Patients who continue to experience clinically significant AEs after a 2-week delay or the maximum allowed number of dose reductions will be discontinued from the study.

Adverse events considered for dose reduction should not include the events assessed by the Investigator as exclusively related to underlying disease or other medical condition or concomitant treatment. A patient who experiences an AE considered related to ALRN-6924 that does not meet the requirement for discontinuation may continue on study if the patient is receiving clinical benefit and/or the Investigator feels continued participation is in the best interest of the patient. In such cases, at the Investigator's discretion and in agreement with Sponsor's Medical Monitor, the dose for a patient may be reduced as described above.

A patient who experiences a DLT must continue treatment at a reduced dose level, or discontinue ALRN-6924 treatment (if Grade 4 related AE), as described above at the discretion of the Investigator and in agreement with Sponsor's Medical Monitor until disease progression or unacceptable toxicity. Once the dose has been reduced for a patient, it may not be re-escalated.

5.8.2 Dose Modifications – Phase 2a dose expansions in PTCL (ALRN-6924 administered as single agent therapy)

In the event a non-hematologic Grade 4 AE considered related to ALRN-6924 is observed, the patient must be discontinued from the study. Exceptions include emesis, diarrhea or electrolyte abnormalities that resolve within 2 days on optimum treatment. For these exceptions, treatment may be delayed for up to 2 weeks to allow resolution of the toxicity (i.e., return to Grade ≤ 1 or baseline), followed by re-treatment at a reduced dose. Relevant labs should be repeated as medically indicated.

In the event a non-hematologic Grade 3 AE considered related to ALRN-6924 is observed (exceptions are Grade 3 fatigue, nausea, emesis, diarrhea or clinically insignificant electrolyte abnormalities that resolve within 2 days on optimum treatment), treatment may be delayed for up to 2 weeks to allow resolution of the toxicity, followed by re-treatment at a reduced dose. Relevant labs should be repeated as medically indicated.

For hematologic toxicities, patients must discontinue treatment with ALRN-6924 if

- Neutrophil counts $< 0.5 \times 10^9/L$ for > 5 days, or
- Platelet counts $< 10 \times 10^9/L$, or
- Hemoglobin $< 6\text{g/dL}$ (despite RBC transfusion or Erythropoiesis-Stimulating Agent (ESA) administration)

Patients must interrupt treatment if

- Neutrophil counts $< 0.5 \times 10^9/L$ for ≤ 5 days, or
- Platelet counts $< 25 \times 10^9/L$ and $> 10 \times 10^9/L$, or
- Hemoglobin $< 8\text{ g/dL}$ and $> 6\text{ g/dL}$

After resolution of hematologic toxicity (i.e., return to Grade ≤ 1 or baseline), patients may continue at a reduced dose. Relevant labs should be repeated as medically indicated.

Following related Grade 3 and Grade 4 AEs (as permitted), the dose for re-treatment will be reduced by 25% intervals (e.g., if the dose is 3.1 mg/kg, the dose will be reduced sequentially to 2.3 mg/kg and 1.7 mg/kg). Two dose reductions are permitted, a third dose reduction will require evidence of clinical benefit and approval by the Medical Monitor.

5.8.3 Dose Modifications – Phase 2a Dose Expansion in MDM2 Amplified or MDM2/CDK4 Co-amplified Solid Tumors (ALRN-6924 plus palbociclib)

Dose modifications of ALRN-6924 will be as described in Section 5.8.1. Dose modifications of palbociclib should be made in accordance with the current approved US prescribing information.

In the event that palbociclib administration must be discontinued, the patient may continue to receive ALRN-6924 as a study participant until one of the criteria for treatment discontinuation has been met. However, if discontinuation of ALRN-6924 is required, patients will be considered to have discontinued study treatment. Those patients may continue to receive palbociclib treatment at the Investigator's discretion.

